10.8.5.3.2. Serious, Unexpected Adverse Drug Reactions

All ADRs that are both serious and unexpected are subject to expedited reporting to regulatory agencies and will be reported in accordance with Directive 2001.20/EC or as per national regulatory requirements in participating countries. An unexpected ADR is one for which the nature or severity is not consistent with information in the relevant source documents.

The following documents or circumstances will be used (by the Sponsor) to determine whether an adverse event/ADR is expected:

1. For a medicinal product not yet approved for marketing in a country, the Reference Safety Information (RSI) section of a company's current edition of the IB will serve as the source document in that country.
2. Reports that add significant information on specificity or severity of a known, already documented serious ADR constitute unexpected events. For example, an event more specific or more severe than described in the RSI in the IB would be considered "unexpected".

10.8.5.4. BARC Bleeding Criteria Assessment

Based on mild bleeding observed with escalating doses of oral temanogrel when co-administered with aspirin and clopidogrel in healthy adult subjects during Phase 1 studies, administration of single doses of IV temanogrel with DAPT in this study may potentially increase the tendency of bleeding; therefore, the assessment of bleeding will be categorized by the Investigator (or qualified designee) using the BARC definition for bleeding (Mehran 2011) (Table 3). For any bleeding events that occur after discharge and before the Follow-Up phone contact, applicable corresponding medical records should be requested for review by the Investigator (or qualified designee).

Table 3: BARC Definitions for Bleeding

Type	Definition
Type 0	No bleeding
Type 1	Bleeding that is not actionable and does not cause the patient to seek unscheduled performance of studies, hospitalization, or treatment by a healthcare professional; may include episodes leading to self-discontinuation of medical therapy by the patient without consulting a healthcare professional
Type 2	Any overt, actionable sign of hemorrhage (ie, more bleeding than would be expected for a clinical circumstance, including bleeding found by imaging alone) that does not fit the criteria for Type 3, 4, or 5 but does meet at least one of the following criteria: 
 1. Requiring nonsurgical, medical intervention by a healthcare professional. 2. Leading to hospitalization or increased level of care. 3. Prompting evaluation.
Type 3	
 a. Overt bleeding plus hemoglobin drop of 3 to < 5 g/dL^a (provided hemoglobin drop is related to bleed) Any transfusion with overt bleeding. b. Overt bleeding plus hemoglobin drop \geq 5 g/dL^a (provided hemoglobin drop is related to bleed). Cardiac tamponade bleeding requiring surgical intervention for control (excluding dental/nasal/skin/hemorrhoid). Bleeding requiring intravenous vasoactive agents. c. Intracranial hemorrhage (does not include microbleeds or hemorrhagic transformation, does include intraspinal). Subcategories confirmed by autopsy or imaging or lumbar puncture. Intraocular bleed compromising vision.
Type 4	CABG-related bleeding. Perioperative intracranial bleeding within 48 hours. Reoperation after closure of sternotomy for the purpose of controlling bleeding. Transfusion of \geq 5 U whole blood or packed red blood cells within a 48-hour period. ^b Chest tube output \geq 2 L within a 24-hour period.
Type 5	Fatal bleeding 
 a. Probable fatal bleeding; no autopsy or imaging confirmation but clinically suspicious. b. Definite fatal bleeding; overt bleeding or autopsy or imaging confirmation.

^a Corrected for transfusion (1 U packed red blood cells or 1 unit whole blood = 1 g/dL hemoglobin).

^b Cell saver products are not counted.

Note: CABG indicates coronary artery bypass graft. Platelet transfusions should be recorded and reported but are not included in these definitions until further information is obtained about the relationship to outcomes. If a CABG-related bleed is not adjudicated as at least a Type 3 severity event, it will be classified as not a bleeding event. If a bleeding event occurs with a clear temporal relationship to CABG (ie, within a 48-hour time frame) but does not meet Type 4 severity criteria, it will be classified as not a bleeding event.

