10.10. Safety-Related Stopping Criteria

Throughout the study, any bleeding event reported as BARC 3c or greater will pause study enrollment and trigger an ad hoc DSMB meeting. Study enrollment will remain paused until the DSMB has made a recommendation as to whether or not the study can continue.

10.11. DSMB Review: Safety-Related Dose Escalation (Stage A)/Dose Recommendation (Stage B) Criteria

At the completion of each cohort in Stage A the DSMB will use the following safety-related criteria to preclude recommendation of further dose escalation in Stage A and use of an associated dose in Stage B:

- Two or more SAEs or two or more BARC 3b or higher events assessed as related to active study treatment within a cohort.
- Two or more subjects on active treatment within a cohort experience an increase in alanine aminotransferase (ALT) or aspartate aminotransferase (AST) $\geq 3 \times$ upper limit of normal (ULN), or alkaline phosphate (ALP) or total bilirubin $\geq 2 \times$ ULN, following study treatment administration. For subjects with values $\geq 2 \times$ ULN prior to dosing, a 100% increase from pre-dosing value meets the criterion.
- Seizure assessed as related to study treatment in a subject who received active study treatment.

In addition to the safety-related criteria listed above, the DSMB will review overall safety data of each cohort (including AEs, clinical laboratory, and vital sign data) when recommending dose escalation within Stage A and doses for Stage B (Section 11.11).

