11.10.1. Safety Endpoints

The safety endpoints will be analyzed using the Safety Set. The primary safety endpoint of the study is the assessment of TEAEs. All bleeding-related adverse events will be classified using the BARC criteria.

- Incidence of all TEAEs
- Incidence of TEAEs by severity
- Incidence treatment-related TEAEs
- Incidence of bleeding-related TEAEs classified using BARC criteria
- Incidence of adverse events leading to discontinuation (if any)
- Incidence of SAEs (if any)
- Incidence and severity of laboratory abnormalities, and change from Baseline in laboratory values (to include hematology, serum chemistry, and coagulation)
- Incidence of clinically significant vital sign abnormalities and changes from Baseline
- Incidence of clinically significant ECG abnormalities and changes from Baseline

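### The Type 3b row of Table 3 appears to merge two bleeding criteria, so read literally some tamponades and surgically controlled bleeds are tabulated as BARC Type 2 or 3a

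*Combined protocol and SAP*

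**What the plan says.** Section 10.8.5.4 has the investigator or a qualified designee grade bleeding by the BARC definition, citing a consensus report and reproducing the types in Table 3. Within Type 3b, one item reads "Cardiac tamponade bleeding requiring surgical intervention for control (excluding dental/nasal/skin/hemorrhoid", and the bracket then closes. The other 3b items are a bleed-related hemoglobin drop of at least 5 g/dL with overt bleeding, and "Bleeding requiring intravenous vasoactive agents".

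The neighbouring rows matter too. Type 3a covers a hemoglobin drop of 3 to less than 5 g/dL, and also "Any transfusion with overt bleeding". Type 2 takes overt, actionable bleeding that fits no higher type and meets at least one of three conditions. Two of these are "Requiring nonsurgical, medical intervention by a healthcare professional" and "Leading to hospitalization or increased level of care"; the third is that the bleed prompted evaluation.

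The types are used in three places:
- **Section 11.10.1** lists as a safety endpoint "Incidence of bleeding-related TEAEs classified using BARC criteria". Section 11.10 summarizes bleeding by type, stage, cohort and treatment group. The final report contents in the Note to File of 7 October 2022 include Table 4.6.AB, which tabulates TEAEs by BARC classification.
- **Section 10.11** precludes further escalation in Stage A, and use of the associated dose in Stage B, if a cohort has two or more SAEs or "two or more BARC 3b or higher events assessed as related to active study treatment within a cohort".
- **Section 10.10** pauses enrollment at BARC 3c or greater.

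**The concern.** As printed, the 3b item is a single condition: tamponade that needs surgery. The text gives two reasons to think this was not meant.

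- The list of excluded sites (dental, nasal, skin, hemorrhoid) has no function for a pericardial bleed. It makes sense only for a general criterion on bleeding that needs surgery for control.
- Type 2 limits its treatment condition to nonsurgical care, which implies that surgically controlled bleeding belongs higher. Yet no Type 3 line, as printed, covers surgical control of a bleed outside the pericardium.

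Investigators grade from this table, and the protocol describes no central adjudication of bleeding. A site that applies the row literally and a site that infers two criteria could give the same bleed different types. At stake is the accuracy of the bleeding-by-type tables in a trial that adds an antiplatelet agent to DAPT and that treats bleeding as an important safety measure (Section 3.2). To a lesser degree, so is the BARC count in the Stage A criterion.

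**Working it through.** The plan gives no figure that depends on this row, so the check is mainly one of logic. Hypothetical bleeds are graded under Table 3 as printed, and again with the 3b item read as two separate criteria (tamponade; bleeding needing surgical control outside the excluded sites). No Type 4 or 5 condition is assumed in any case.

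| Bleed | As printed | If two criteria |
|---|---|---|
| 1. Tamponade, no surgery; Hb drop < 3 g/dL, no transfusion, no IV vasoactive agent | Type 2 | 3b |
| 2. As 1, but Hb drop 3 to < 5 g/dL or transfusion | 3a | 3b |
| 3. Non-tamponade bleed controlled surgically, outside the excluded sites; Hb drop < 3 g/dL, no transfusion, no IV vasoactive agent | Type 2 | 3b |
| 4. As 3, but Hb drop 3 to < 5 g/dL or transfusion | 3a | 3b |
| 5. Any of 1 to 4 with Hb drop ≥ 5 g/dL or IV vasoactive agents | 3b | 3b |
| 6. Tamponade treated surgically | 3b | 3b |
| 7. Intracranial bleed, or intraocular bleed compromising vision | 3c | 3c |

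Only cases 1 to 4 move. In case 3 the nonsurgical-treatment condition of Type 2 does not apply, but the conditions on hospitalization or level of care and on evaluation bring the bleed into Type 2.

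**Effect on the tabulation.** The synopsis plans 29 subjects per Stage B arm. One event displaced from 3b changes that arm's 3b-or-higher incidence by 1/29 = 0.034, or 3.4 percentage points.

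**Effect on the Stage A criterion.** Each cohort has 4 temanogrel subjects, and the BARC limb needs 2 related events. Suppose two related events occur that would both be 3b under the two-criterion reading, and one is displaced. The BARC count is 2 − 1 = 1, so that limb is not met. The SAE count does not depend on BARC type. If both events are SAEs it is 2, and the Section 10.11 criterion is still met. Section 10.8.5.1.2 makes an event serious if it is life-threatening, requires or prolongs hospitalization, or is medically significant. Bleeds of the kind in cases 1 to 4 would usually qualify.

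**Effect on the enrollment pause.** None: the threshold is 3c, and case 7 is the same under both readings.

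**Could this be a line break lost when the PDF was read?** The missing full stop proves nothing, because row 3a also runs two items together without one. There, however, the second item keeps its capital letter. In the 3b item the word bleeding is in lower case, while the next item starts with a capital. A lost line break would not change the case of a letter.

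**The case against.** The strongest reply is that this is a copying slip in one table row with little consequence. Section 10.8.5.4 points investigators to the cited definition, so many may grade correctly anyway. BARC-typed bleeding is one of nine listed safety endpoints and is summarized without a planned test, and the primary safety endpoint is the assessment of TEAEs. The 3.4 points is simply one assumed event over 29; the documents give no expected rate for the displaced patterns. Enrollment was stopped after the decision of 25 August 2022, the database was locked on 10 October 2022, and nothing shows that an affected bleed occurred.

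Most of this stands as a limit on size. It does not make the row correct. Table 3 is the grading text in the protocol, and its output is still planned for the final report.

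A reader might also infer that these bleeds always fall below 3b, or that one misgraded event defeats the Stage A criterion. The documents support neither. A hemoglobin drop of at least 5 g/dL or a need for IV vasoactive agents keeps a bleed at 3b. The same Section 10.11 bullet carries the SAE limb, and Sections 10.11 and 11.11 have the DSMB review each cohort's wider safety data, unblinded.

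**Conclusion.** The point holds as a probable transcription defect in the Type 3b row, and it is worth correcting. Its main effect is on bleeding tabulated by BARC type, where cases 1 to 4 would be reported as Type 2 or 3a. At planned numbers each such event is worth 3.4 points in a Stage B arm. The documents do not say how many subjects were enrolled when the study stopped; with fewer than 29 in an arm, one event would weigh more. In Stage A only the BARC limb of the escalation criterion is exposed, and the criterion as a whole would usually still be met.

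This rests on three assumptions: that a site applies the row literally, that the lower-case wording is in the protocol and not an effect of text extraction (unlikely, but not fully excluded), and that such bleeds would normally be SAEs. The cited BARC source was not available, so the conclusion that two criteria were merged rests on the protocol's own wording alone.

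**What to change.** Reconcile the Type 3b row of Table 3 with the BARC definition the protocol cites and with the 3b threshold in Section 10.11. If the source confirms two criteria, print them separately and attach the site exclusions only to the one they belong to. Use the same text in the eCRF guidance and the DSMB output specifications.

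Because enrollment has ended, the useful step now is to re-check the assigned type of every recorded bleed against the reconciled wording before relying on Table 4.6.AB, and to state in the report which wording was used for grading.

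The cost is one table row, matching help text and a short re-review of recorded bleeding events. The count of 3b events may rise slightly.

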10.8.6. Pregnancy

Women of childbearing potential may not participate in this study. Details of all pregnancies that occur in female subjects and female partners of male subjects that begin between the study treatment administration and 90 days after treatment administration will be collected.

Pregnancy (during maternal or paternal exposure to study treatment) does not meet the definition of an adverse event; however, to fulfill regulatory requirements, any pregnancy and/or pregnancy outcome should be reported via the Pregnancy Report Form to the designated Sponsor Contact **within 24 hours of awareness.**

Abnormal pregnancy outcomes (eg, spontaneous abortion, fetal death, stillbirth, congenital anomalies, ectopic pregnancy) are considered SAEs and should be reported as such even if outside the SAE reporting period.

10.9. Order of Events and Priority for Timed Assessments

Every effort should be made to perform procedures as closely as possible to the scheduled times indicated in the Schedule of Assessments ([Appendix 1](#)).

On Day 1, the timing of events should first be determined by subject safety requirements and then by the scheduled times and sequential order of events as described in this protocol, giving consideration to appropriate posture conditions, practical restrictions, and the other procedures scheduled to be performed at the same timepoint. The preferred order of events in the Peri-PCI period is as follows:

1. Diagnostic angiography including confirmation of lesion-related eligibility (not required if a diagnostic angiography obtained within 60 days prior to Day 1 confirms lesion characteristics)
2. Randomization
3. Baseline peripheral blood draw
4. Baseline target vessel angiographic measures (not required to be repeated if completed during diagnostic angiography at Check-in; in cases when diagnostic angiography is not performed at Check-in, lesion and vessel characteristics should be assessed as part of Baseline target vessel angiographic measures assessment prior to administration of study treatment)
5. Baseline coronary physiology indices (IMR, CFR, FFR; not required to be repeated if completed at Check-in for confirmation of suitability for PCI per institutional standards)
6. Treatment administration
7. Post-treatment / pre-PCI peripheral blood draw (collected 0-2 minutes after the end of the IV administration of randomized study treatment)
8. Post-treatment / pre-PCI coronary physiology indices (IMR, CFR, FFR)
9. PCI with predilation (if applicable) and stent deployment
10. Post-PCI (within 15 minutes of the completion of the PCI procedure) coronary artery (coronary ostium and coronary artery distal to the lesion) blood sampling

11. Post-PCI (within 15 minutes of the completion of the PCI procedure) coronary physiology indices (IMR, CFR, FFR)
12. Post-PCI (within 15 minutes of the completion of the PCI procedure) target vessel angiographic measures
13. Post-PCI (within 15 minutes of the completion of the PCI procedure) peripheral blood draw

Specific timing of the study activities listed above is not critical (unless specified) as long as activities are completed in the order specified.

10.10. Safety-Related Stopping Criteria

Throughout the study, any bleeding event reported as BARC 3c or greater will pause study enrollment and trigger an ad hoc DSMB meeting. Study enrollment will remain paused until the DSMB has made a recommendation as to whether or not the study can continue.

10.11. DSMB Review: Safety-Related Dose Escalation (Stage A)/Dose Recommendation (Stage B) Criteria

At the completion of each cohort in Stage A the DSMB will use the following safety-related criteria to preclude recommendation of further dose escalation in Stage A and use of an associated dose in Stage B:

- Two or more SAEs or two or more BARC 3b or higher events assessed as related to active study treatment within a cohort.
- Two or more subjects on active treatment within a cohort experience an increase in alanine aminotransferase (ALT) or aspartate aminotransferase (AST) $\geq 3 \times$ upper limit of normal (ULN), or alkaline phosphate (ALP) or total bilirubin $\geq 2 \times$ ULN, following study treatment administration. For subjects with values $\geq 2 \times$ ULN prior to dosing, a 100% increase from pre-dosing value meets the criterion.
- Seizure assessed as related to study treatment in a subject who received active study treatment.

In addition to the safety-related criteria listed above, the DSMB will review overall safety data of each cohort (including AEs, clinical laboratory, and vital sign data) when recommending dose escalation within Stage A and doses for Stage B (Section 11.11).

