Stage A is an ascending single-dose study planned to consist of 2 cohorts. After treatment of each cohort in Stage A, a safety/tolerability assessment will be conducted by the Data and Safety Monitoring Board (DSMB). Following the safety review of the first cohort in Stage A, the DSMB will recommend whether dose escalation to the next planned dose level in Stage A should occur; the DSMB may also recommend evaluation of an alternative dose in the second cohort in Stage A. Following the safety review of the second cohort in Stage A, the DSMB will recommend whether progression to Stage B should occur; the DSMB may also recommend evaluation of an alternative dose in an additional third dose cohort in Stage A prior to progression to Stage B. After conduct of the final cohort and safety review of Stage A, Stage B may begin. Stage B is a parallel-treatment group study planned to consist of a placebo group and 2 active treatment groups (temanogrel doses selected based on safety and tolerability data in Stage A). In Stage B, enrollment will consist of no more than 25% elective PCI subjects and randomization will be stratified subject type (elective PCI or PCI for non-ST-elevation myocardial infarction [NSTEMI]/unstable angina [UA]).

Subjects should be treated with aspirin and an oral P2Y₁₂ inhibitor (ie, dual antiplatelet therapy [DAPT]) per site standard of care; however, subjects in Stage A may only be treated with clopidogrel as the P2Y₁₂ inhibitor DAPT component and may not be treated with prasugrel or ticagrelor until after the subject has completed study participation.

Number of subjects (planned):

Approximately 99 subjects are planned to be enrolled in this study. In Stage A, 2 cohorts are planned and approximately 6 subjects will be enrolled in each cohort (4 temanogrel:2 placebo per cohort). One additional cohort (4 temanogrel:2 placebo per cohort) may be enrolled to explore an additional dose if deemed appropriate based upon data reviews of prior cohorts. In Stage B, approximately 87 subjects are planned to be enrolled (29 subjects in each of the 2 temanogrel treatment groups and the placebo group).

Eligibility criteria:

Inclusion criteria:

Subjects must meet ALL of the following inclusion criteria to be eligible for enrollment into the study:

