Convulsions were noted in rats following a single IV (bolus) at ≥ 60 mg/kg temanogrel, and generalized seizures in monkeys at oral doses ≥ 100 mg/kg/day temanogrel. The no-observed-adverse-effect levels (NOAELs) in these studies were 20 mg/kg (acute IV rat study) and 35 mg/kg/day (oral 4-week monkey study). Similar nervous system-related findings have not been observed with temanogrel administration to healthy subjects at exposure margins of at least 2.3-fold following a single 320 mg oral dose (based on the lowest C_{max} at the oral 4-week monkey study NOAEL) and 7.3-fold following a single 40 mg IV dose (based on the lowest C_{max} at the acute IV rat study NOAEL).

Additional risks of participation in the study are primarily those associated with adverse reactions to the study treatments, although there may also be some discomfort from collection of blood samples and other study procedures. Further description of identified risks, any potential risks, and the reference safety information for temanogrel are provided in the current edition of the IB.

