10.8.5.1.6. Relationship

The Investigator is obligated to assess the relationship (causal relationship) between the study treatment and each occurrence of each adverse event. The adverse event relationship (causal relationship) to study treatment must be characterized as one of the following categories:

- Not Related:** The adverse event does not follow a reasonable temporal sequence from administration of the drug, does not abate upon discontinuation of the drug, does not follow a known or hypothesized cause-effect relationship, and (if applicable) does not reappear when the drug is reintroduced, furthermore, there may exist a clear alternative medical explanation (ie, underlying disease state) or association with study procedure or study conduct.
- Unlikely Related:** The temporal association between the adverse event and the drug is such that the drug is not likely to have any reasonable association with the adverse event.
- Probably Related:** The adverse event follows a reasonable temporal sequence from administration of the drug and cannot be reasonably explained by the known characteristics of the subject's clinical state, environmental, or toxic factors, or other modes of therapy administered to the subject.
- Related:** The adverse event follows a reasonable temporal sequence from administration of the drug, abates upon discontinuation of the drug, follows a known or hypothesized cause-effect relationship, and (if appropriate) reappears when the drug is reintroduced.

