10.13. Procedures for Overdose

Overdose is not expected as study treatment will be administered in a highly controlled environment by qualified designees at the study centers. The Sponsor does not recommend

specific treatment for an overdose; there is no known antidote to temanogrel. After an overdose or suspected overdose, subjects should be monitored for adverse events.

If a subject receives a dose in excess of the instructed dose (eg, due to pharmacy error) and if symptoms are present, the Investigator or designee should contact the Medical Monitor immediately. In the absence of associated adverse events as assessed per the clinical judgement of the Investigator, no further action is required.

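### A treatment-related seizure on active drug can bar a dose by itself, yet only a severe bleed pauses enrolment automatically; the seizure criterion waits for the end of the Stage A cohort

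*Combined protocol and SAP*

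**What the plan says.** Protocol section 10.10 is the stopping-criteria section. It holds one rule, which applies throughout the study and carries no relatedness condition: "any bleeding event reported as BARC 3c or greater will pause study enrollment and trigger an ad hoc DSMB meeting". Enrolment then stays paused until the DSMB makes a recommendation. Section 11.11 restates the rule and adds no other automatic pause.

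Section 10.11 lists criteria that stop escalation in Stage A and keep the dose out of Stage B. It opens: "At the completion of each cohort in Stage A the DSMB will use the following safety-related criteria". One criterion is met by a single event: "Seizure assessed as related to study treatment in a subject who received active study treatment". The others need at least two, for example "Two or more SAEs or two or more BARC 3b or higher events assessed as related to active study treatment within a cohort" and the liver-test criterion, which needs two or more subjects. Section 11.11 likewise places the Stage A unblinded review at the completion of each cohort.

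On cohort size, the synopsis says "approximately 6 subjects will be enrolled in each cohort (4 temanogrel:2 placebo per cohort".

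Section 1.2 gives the animal signal ("Convulsions were noted in rats following a single IV (bolus", at 60 mg/kg or more, and generalized seizures in monkeys at oral doses of 100 mg/kg/day or more). Section 10.13 states that "there is no known antidote to temanogrel". On causality, section 10.8.5.1.6 says: "The adverse event relationship (causal relationship) to study treatment must be characterized as one of the following categories". The categories are Not Related, Unlikely Related, Probably Related and Related.

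**The concern.** The two sections rank events differently. Under 10.11, one related seizure on active drug disqualifies a dose, whereas one BARC 3c bleed does not meet the bleeding criterion, which needs two related events. Under 10.10, the 3c bleed stops enrolment at once and the seizure does not. The event that the protocol treats as decisive by itself has no automatic response when it happens.

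This matters because each subject receives one IV bolus that cannot be withdrawn. If a related seizure occurs early in a cohort, whether the next subject receives the same dose before the DSMB has looked depends on someone choosing to intervene. The protocol describes no sentinel dosing and no minimum interval between subjects in a cohort.

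**Working it through.** The documents state no operating characteristic for the stopping rules, so there is no published figure to reproduce. The check is a comparison of the text followed by a count.

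**Text comparison**

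| | BARC 3c or greater bleed | Related seizure on active drug |
|---|---|---|
| Bars a dose by itself (10.11) | No, two related events needed | Yes |
| Pauses enrolment automatically (10.10, 11.11) | Yes | No |
| When the protocol requires DSMB action | At once, ad hoc | At completion of the Stage A cohort |

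**Count of further exposure in Stage A**

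Input: 4 active and 2 placebo subjects per cohort (synopsis). Subjects are taken as dosed one at a time. The seizure occurs in the active subject at position k, where k = 1 to 4, and each position is equally likely. L is the number of further active subjects dosed before the seizure is known and judged related. The documents give no dosing interval, so L is an assumption and is shown over a range.

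Active subjects who could still be dosed afterwards = max(4 − k − L, 0).

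| L | k = 1, 2, 3, 4 | Mean | Maximum |
|---|---|---|---|
| 0 | 3, 2, 1, 0 | 6/4 = 1.5 | 3 |
| 1 | 2, 1, 0, 0 | 3/4 = 0.75 | 2 |
| 2 | 1, 0, 0, 0 | 1/4 = 0.25 | 1 |
| 3 | 0, 0, 0, 0 | 0 | 0 |

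These figures are conditional on a seizure and use no event rate. Equal likelihood of position is the rare-event case. If instead each active subject has an independent seizure probability p, the mean at L = 0 is Σ(1 − p)^(k−1) · p · (4 − k) ÷ [1 − (1 − p)^4]. For assumed p of 0.05 this is 0.2901/0.1855 = 1.56, and for 0.30 it is 1.467/0.7599 = 1.93. These rates are illustrative only, and the maximum stays at 3.

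**Cost of a blinded seizure trigger**

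If the drug has no effect on seizures, the share of pauses caused by a placebo subject equals the placebo share of subjects: 2/6 = 0.33 in a Stage A cohort and 29/87 = 0.33 in Stage B.

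**The case against.** The strongest reply is that the protocol leaves several routes open and that the charter has not been seen. Section 11.11 places the safety review criteria in a separate DSMB charter and provides for ad hoc review. A drug-related seizure would plausibly qualify as an SAE and so reach the sponsor within 24 hours (10.8.5.3.1). The sponsor can put the study on hold (8.4), and an investigator may depart from the protocol to remove an immediate hazard (12.5). All of this stands. A reader might infer that subjects would in fact go on being dosed after a seizure, or that nothing protects them. The documents do not support that. What remains is narrower: no route in the protocol is tied to seizure or requires a pause. The same routes were available for BARC 3c bleeds, and an automatic rule was written for those anyway.

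A second reply is that the event is unlikely. Healthy subjects showed no similar findings, with an exposure margin of at least 7.3-fold after 40 mg IV relative to the rat no-effect level (1.2). Doses cannot exceed 40 mg (6.3), and any seizure history is excluded (4.2). This also stands, and it sets the severity.

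A reader might extend the point to two related BARC 3b events. That extension is not justified. A bleed of 3c or greater already pauses enrolment, so the gap arises only when the second event is type 3b. The criterion needs two events, as do the SAE-count and liver criteria, and nothing in the text singles it out. A blinded trigger would also be imprecise: of C(6,2) = 15 pairs of different subjects, only C(4,2) = 6 are both active, so 9/15 = 60% of such pauses would not meet 10.11 if the drug had no effect.

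Finally, a trigger based on the investigator's causality call still involves judgement. That is true, but 10.11 already relies on relatedness, and 10.8.5.1.6 requires an initial causality call before an SAE report is first sent. The judgement is therefore available in time.

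**Conclusion.** The point holds for seizure, as a low-severity improvement to the protocol text. Read literally, the protocol permits up to 3 of 4 active subjects in a Stage A cohort to receive a dose that already meets a barring criterion. The mean is 1.5 if the event is known before the next active dose, falling to 0.75 or 0.25 with a lag of one or two active subjects. This assumes sequential dosing and equal likelihood of position, and it is conditional on an event that is probably rare.

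A reader might conclude that Stage B breaches 10.11. It does not, because 10.11 is written for Stage A cohorts. In Stage B the protocol text has no seizure rule and defers to the charter for the timing of reviews. The conclusion covers the protocol only; the charter may already contain a seizure trigger. The Note to File of 7 October 2022 records that enrolment was terminated after the decision of 25 August 2022, so the correction concerns the plan as written and any reuse of it.

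**What to change.** Add one sentence to 10.10 and repeat it in 11.11: any seizure that the blinded investigator assesses as Probably Related or Related to study treatment also pauses enrolment and triggers an ad hoc unblinded DSMB meeting.

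- **Stage A:** the DSMB then decides whether the 10.11 seizure criterion is met, which depends on whether the subject received active drug.
- **Stage B:** 10.11 does not apply, so the DSMB recommends whether the study and the dose can continue, following the mechanism that 10.10 already uses for bleeds.

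State that the blinded trigger is deliberately broader than 10.11, since it can fire for a placebo subject. Check the charter first. If it already has this trigger, cite it in 10.10; if not, add a matching line. No change is proposed for the BARC 3b, SAE-count or liver criteria.

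The cost is two sentences, possibly a charter line, and an occasional short pause, about 1 in 3 of them for a placebo subject if the drug has no effect. No running unblinded tally is needed. The existing BARC 3c trigger has no relatedness condition, so the plan already accepts pauses that may prove to concern placebo.
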